All LVAD candidates at Massachusetts General Hospital (MGH) will be screened for trial eligibility. Every eligible candidate will be asked to participate. Subjects who consent to the study will undergo pre-operative or intra-operative placement of an RVAD, which will be left in up to 72 hours postoperatively. If it is determined that a subject requires support for longer than 72 hours, the treating physician will consider utilizing a more durable form of right ventricular support (CentriMag paracorporeal RVAD requiring direct cannulation), as is standard practice. The type of RVAD (Impella RP or ProtekDuo) inserted will be determined by patient needs and venous access and will be up to the discretion of the treating physician. The use of the ProtekDuo will be prioritized due to the benefit of the jugular approach in device placement, which does not limit patient mobility. If there is no jugular access, the Impella RP, which is placed through a femoral approach, will be used. We aim to enroll 25 subjects in the prospective interventional cohort, and compare to 25 subjects in the matched retrospective control cohort.

All enrolled patients in the prospective interventional cohort will undergo surgical placement of a percutaneous RVAD within 48 hours preoperatively to LVAD implantation, at the time of LVAD implant, or immediately following the implant. After removal of the RVAD, subjects will receive standard treatment according to MGH's standard of care. Data will be obtained for subjects in both cohorts from the electronic medical record in EPIC at MGH and will be reviewed throughout the study through the 1-year follow-up period. Other standard of care tests are administered regularly at LVAD follow-up visits, including: the KCCQ-12 and EQ-5D surveys, a neurocognitive trailmaking test, and a six-minute walk and gait speed test. These are collected per standard of care at the following timepoints: pre-implant, 3 month (+/- 30 days), 6 month (+/- 60 days), and 1 year (+/- 60 days). These results will also be collected and entered to the study database.

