Past medical history will be assessed at the time of screening and documented at the time of enrollment. Data collected will relate to underlying cardiovascular pathology and to associated pathology of the pulmonary, renal, hepatic, endocrine, hematologic, or neurologic systems.

Medications

Data on both active and past medications will be collected at the time of initial screening. If the patient is admitted at the time of screening, both current inpatient medications and home medications will be recorded. If the patient is outpatient at the time of screening, home medications will be recorded. Record of active medications will also be collected at each timepoint throughout the study.

Laboratory Data

Pre- and post-operative lab data including but not limited to CBC, CMP, INR, NT-pro-BNP will be collected at various timepoints during the study, including at time of enrollment.

EKG, ECHO, and Cardiac Catheterization assessment

EKG, ECHO, and Cardiac Catheterization results will be collected at several points during the study.

Inpatient Events/Procedures

Data on events and procedures that occur while patients are admitted will be collected on an ongoing basis while study participants are admitted to the hospital. Where complications occur, adverse event forms will be completed and principal investigators will be notified.

PRIMARY ENDPOINT

The primary outcome of the study will be the vasoactive inotropic score (VIS). Both the average/mean VIS and the cumulative VIS over the first 24 hours post-LVAD implantation of the experimental cohort (those enrolled in the prospective study who undergo pre-emptive RVAD placement) will be compared to a historical cohort of patients who received the current standard of care. The VIS will be calculated for each patient in both arms of the study. Both the maximum score and the cumulative sum achieved in the first 24 hours after LVAD implantation will be recorded (maximal 24-hour VIS and cumulative 24-hour VIS).

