The primary analysis will be performed in an intention-to-treat fashion using a two-sided T-test (alpha level=0.05). The null hypothesis is that the mean maximal 24-hour VIS will not differ between intervention and historical groups. The alternate hypothesis is that compared to standard of care (historical cohort), placement of an RVAD within 48 hours before or during LVAD implantation will decrease the mean maximal 24-hour VIS score by 50%. Analysis assumptions will include independence of study groups and lognormal (or normal) distribution of data in each group.

SECONDARY OUTCOMES

Secondary end points will include:

- Total VIS (throughout hospitalization)
- ICU length of stay (LOS)
- Total post-operative LOS after LVAD implantation
- Survival at discharge after LVAD placement
- Survival at 1 year after LVAD placement or heart transplant
- End organ dysfunction including
 - o Development of acute kidney injury (AKI) – defined as increase in serum creatinine (sCr) to 4mg/dl or greater, a 150% or greater increase in sCr over the baseline preoperative value, or a new requirement for renal replacement therapy
 - o Liver dysfunction
- LVAD device speed

Cox proportional hazard models (one sided, 0.05 significance level) will be used to compare rates of secondary outcomes between intervention and historical arms. Event rates and relative risks will also be estimated for each of these outcomes.

POWER ANALYSIS

Sample size calculations are estimated based on expected effect size, which was determined based on expert consensus (reduction in the mean maximal 24-hour VIS score by 50% in the intervention arm compared to the historical controls). 80% power will be generated with 2-tailed confidence interval of 0.05 from a sample size of 34 patients (17 per group). Estimating a

standard deviation of 0.5 of the outcome in the population and 20% attrition and/or cross-over, investigators anticipate that 20 patients will be needed to test this hypothesis. This power estimation assumes a lognormal distribution of the data. We plan to allow for 25 patients to participate in the prospective arm of the study to allow for incorrect assumptions.

IX. RISKS AND DISCOMFORTS

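### The primary comparison counts only enrolled subjects who receive an RVAD, yet the primary analysis is labelled intention-to-treat; the two rules differ for anyone who reaches LVAD implantation without the device

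*Protocol*

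**What the plan says.** Four places in the protocol bear on who is counted.

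- **Section VIII, Primary Endpoint, first paragraph.** The experimental cohort to be compared with the historical cohort is glossed as "those enrolled in the prospective study who undergo pre-emptive RVAD placement". This sets two conditions: enrolled, and device placed.
- **Section VIII, Primary Endpoint, second paragraph.** "The primary analysis will be performed in an intention-to-treat fashion using a two-sided T-test (alpha level=0.05". Only one arm is prospective, so intention-to-treat can only mean keeping enrolled subjects whether or not they received the device.
- **Section VI, Study Procedures.** "All enrolled patients in the prospective interventional cohort will undergo surgical placement of a percutaneous RVAD within 48 hours preoperatively to LVAD implantation", or at the time of the implant or directly after it. On this expectation the two sets are the same people.
- **Section VIII, Power Analysis.** The calculation assumes a "standard deviation of 0.5 of the outcome in the population and 20% attrition and/or cross-over". Attrition and cross-over are not separated.

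Section VIII, Study Variables, matches controls to the enrolled prospective subjects and defines controls by a past LVAD implantation without a percutaneous RVAD. Nothing in the protocol says which rule governs an enrolled subject who has the LVAD implanted but no RVAD placed.

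**The concern.** Adjacent paragraphs give two definitions of the set behind the primary result. They agree only if every enrolled subject who reaches LVAD implantation also receives an RVAD. The allowance for cross-over shows that the investigators did not take that for granted.

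Two things are at stake. First, the estimates answer different questions: one is the effect of planning a preemptive RVAD, the other the effect among those in whom it was placed. Second, the controls are historical, so no randomisation protects a cohort trimmed after consent. If the reason a device was not placed is related to how much inotropic support the subject would need, removing that subject disturbs comparability with the controls. Controls were matched to enrolled subjects, so a treated-only set also leaves some controls without their match.

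**Working it through.** **Inputs.** Planned size is 25 prospective subjects and 25 matched controls (section VI). From the Power Analysis come the effect, "reduction in the mean maximal 24-hour VIS score by 50% in the intervention arm compared to the historical controls", the standard deviation of 0.5, and the 20% allowance. Two-sided alpha is 0.05.

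**The plan's own figure.** The protocol states that "80% power will be generated with 2-tailed confidence interval of 0.05 from a sample size of 34 patients (17 per group"). Reading the 50% as a difference of 0.5 gives a standardised effect of 0.5 / 0.5 = 1.0. A two-sample t-test then needs 16.7, so 17 per group, with power 80.7% at 17. The figure is reproduced, and the same scale is used below.

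**How many subjects the rules treat differently.** Let f be the share of enrolled subjects who undergo LVAD implantation without an RVAD. The protocol does not give f. If the 20% is all attrition, f = 0; if it is all cross-over, f = 20%, and 0.20 × 25 = 5 subjects. The range is 0 to 5 of 25.

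**Dilution.** Assume that recipients' scores are halved and that non-recipients score as controls do.

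- Arithmetic mean ratio under intention-to-treat: (1 − f) × 0.5 + f × 1.0. At f = 20% this is 0.8 × 0.5 + 0.2 × 1.0 = 0.60, a 40% reduction.
- Geometric mean ratio: 0.5 raised to the power (1 − f). At f = 20% this is 0.574, a 43% reduction.
- Treated-only: 0.50 on either scale, whatever f is.

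For power, the intention-to-treat difference is d(1 − f), and the variance in the prospective arm is 0.25 + f(1 − f)d². The d = 0.5 column follows the protocol's scale. The d = ln 2 column reads the 50% as a true halving on the log scale with standard deviation 0.5. Both use 25 controls.

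| f | Prospective n, ITT / treated-only | ITT reduction, arithmetic | ITT reduction, geometric | Power, d = 0.5, ITT / treated-only | Power, d = ln 2, ITT / treated-only |
|---|---|---|---|---|---|
| 0% | 25 / 25 | 50% | 50% | 93% / 93% | 99.8% / 99.8% |
| 10% | 25 / 22 | 45% | 46% | 86% / 92% | 98.6% / 99.6% |
| 20% | 25 / 20 | 40% | 43% | 76% / 90% | 94.7% / 99.5% |

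(10% of 25 is 2.5; 22 recipients were used.)

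**Selection.** The table shows dilution, not bias. For bias, suppose instead that the enrolled group as a whole would have had control-level scores without the device, that f = 20%, and that the device halves recipients' scores. The two levels chosen for non-recipients are illustrations.

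- Non-recipients at 0.3 of control: recipients' untreated level is (1 − 0.2 × 0.3) / 0.8 = 1.175. Halved, this is 0.5875, so treated-only shows a 41% reduction and understates the true 50%.
- Non-recipients equally far above control, at 1.7: (1 − 0.2 × 1.7) / 0.8 = 0.825. Halved, this is 0.4125, so treated-only shows 59% and overstates it.

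**The case against.** The best defence is that the parenthesis merely describes the arm, to tell it apart from the historical cohort. Section VI expects all enrolled subjects to receive the device, controls are matched to enrolled subjects, and the only sentence that states an analysis principle says intention-to-treat. On that reading the principle governs, and detailed analysis-set rules can be left to a statistical analysis plan. This is a fair reading and probably the intended one. But the protocol does not leave the matter open: it states both rules, and the narrower one sits in the definition of the primary comparison.

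A reader might infer more than the text supports:

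- **That non-receipt will occur, in 5 subjects.** The 20% is an undivided planning allowance. Subjects lost before LVAD implantation have no post-LVAD score under either rule, so only the cross-over part separates the two sets, and that part may be zero.
- **That the treated-only estimate overstates the effect.** The direction depends on why the device was not placed, as the two illustrations show.
- **That the device may be withheld because the right ventricle looks adequate.** The protocol has no such provision. Patients without echocardiographic right ventricular dysfunction, or with venous access that precludes or complicates placement, are excluded at entry, and a second access route is provided. A failed or abandoned placement remains conceivable, but its frequency is not given.
- **That the protocol allows a treated-only result to be reported as intention-to-treat.** The intention-to-treat sentence speaks against that. The fault is ambiguity, not permission.

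**Conclusion.** The point stands as an internal contradiction about who enters the primary analysis. Its practical size runs from nothing, if every enrolled subject who reaches LVAD implantation has the RVAD placed, to 5 of 25 prospective subjects. At that upper end, with control-level scores in non-recipients, the same data would show about a 40% reduction under one rule and 50% under the other (43% against 50% on the geometric scale). On the protocol's planning scale, power would be about 76% against 90%, on opposite sides of the 80% target; if the 50% is read as a halving on the log scale, power stays above 90% under both. These sizes rest on the assumed scores of non-recipients and on taking the whole allowance as cross-over. The conflict between the two sentences rests on no assumption. It should be corrected, because the comparison is not randomised and the correction is cheap.

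**What to change.** In section VIII, Primary Endpoint, replace the parenthesis so that the experimental cohort for the primary comparison is *all enrolled prospective subjects who undergo LVAD implantation, whether or not the RVAD was placed*. This parallels the controls, who are defined by having had an LVAD implanted.

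Add two statements:

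- Enrolled subjects who never reach LVAD implantation are listed separately, because a 24-hour post-LVAD score does not exist for them. The list shows which of them had already received an RVAD. This matters because the device may be placed up to 48 hours beforehand, so a subject could be treated and still fall outside the primary set. The list discloses that selection but does not remove it.
- The subset with a device placed is reported only as a labelled secondary analysis.

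The change is to wording alone and needs no extra patients or data. Its downside is that the primary estimate may be somewhat smaller, with less power, if some subjects go without the device.

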(CI), which results in the improvement of systemic and end-organ perfusion, as well as the reversal of cardiogenic shock. Impella RP placement has also been shown to decrease central venous pressure (CVP) (Anderson). This improvement in hemodynamics facilitates the weaning of inotrope and vasopressor support. LVAD flow has also been shown to improve after Impella RP support is initiated (Anderson).

ProtekDuo, manufactured by TandemLife, is another device placed percutaneously for right heart support via the right internal jugular (RIJ) vein. Like the Impella RP, use of the ProtekDuo is associated with improved hemodynamics in patients with right ventricular failure. Studies looking at concomitant insertion of the ProtekDuo and LVAD to preempt RVF in patients with impaired RV function have shown advantageous effects on patient outcomes compared to insertion post-LVAD (Schmack). It is expected that preemptive placement of RVADs prior to or during LVAD implantation to preemptively treat RVF will similarly result in improved patient outcomes.

III. SPECIFIC AIMS

The purpose of this study is to compare clinical outcomes of standard of care treatment versus preemptive percutaneous right ventricular assist device (RVAD) placement surrounding left ventricular assist device (LVAD) implantation. We hypothesize that the use of the RVAD will mitigate need for inotropic support, reducing the vasoactive-inotrope score (VIS) by 50%, and will improve end organ function in patients compared to standard of care.

IV. SUBJECT SELECTION

This trial will include both a prospective interventional cohort and a retrospective control cohort. The prospective interventional cohort will consist of patients undergoing LVAD implantation at Massachusetts General Hospital. These patients will receive an RVAD (either the ProtekDuo or Impella RP) prior to or during LVAD implantation. The historical control cohort will consist of retrospective data collection on patients who have undergone LVAD implantation in the past. This group will be age and sex matched with the enrolled prospective interventional patients.

INCLUSION:

- Ages 18-75
- Accepted for LVAD implantation by MGH multidisciplinary team

EXCLUSION:

- Disorders of the pulmonary artery wall that would preclude placement or correct positioning of RVAD
- Presence of mechanical valves
- Mural thrombosis of the right atrium or vena cava
- Anatomic conditions precluding insertion of the RVAD

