Clinical data will be collected and entered into the secure database by study coordinators. All subjects will be followed through 12-month post-LVAD implantation with data collection occurring at the following timepoints: pre-implant, time of implant, discharge, 1 week (+/- 3 days), 1 month (+/- 7 days), 3 month (+/- 30 days), 6 month (+/- 60 days), and 1 year (+/- 60 days), all of which will align with routine clinical standard of care visits. Subjects will not be asked to come for additional visits separate from their usual standard of care visits. All follow-up tests and procedures will also be done per standard of care.

VII. DATA COLLECTION SCHEDULE

DATA COLLECTION SCHEDULE									
ASSESSMENT	Pre-LVAD Implant	RVAD Placement	LVAD Implant	1 Week Follow-up	Implant Discharge	1 Month Follow-up	3 Month Follow-up	6 Month Follow-up	1 Year Follow-up
Screening	X								
Demographics	X								
Medical History	X								
RVAD Placement Details		X	X						
LVAD Implant Details			X						
Discharge Details					X				
Status	X			X		X	X	X	X
Right Heart Failure Assessment				X		X	X	X	X
Hemodynamics	X			X		X	X	X	X
Medications	X			X	X	X	X	X	X
Laboratory	X			X		X	X	X	X
Device Details							X	X	X
Exercise/Trailmaking	X						X	X	X
Quality of Life	X						X	X	X
Adverse Events		X	X	X		X	X	X	X

VIII. BIostatistical Analysis

STUDY VARIABLES

Eligibility Data

Potential study participants who have left-heart failure and are planned to undergo LVAD placement will be approached by the study staff. The study will be explained, and these potential participants will be provided with study information and consent forms. Potential participants who meet study criteria will be assigned a unique identifier at this time (regardless if they are enrolled, which will ensure accurate recording of number of screened vs. enrolled patients). Enrolled subjects in the prospective arm will be matched to historical controls, which will consist of patients who underwent LVAD implantation in the past in the absence of pre-operative or concurrent percutaneous RVAD placement.

Demographics – collected at outpatient visit when patient is being considered for LVAD placement
Demographic data assessed and recorded at the initial screening visit will include date of birth, gender, race, and ethnicity.

Comorbidities

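### The primary t-test against age- and sex-matched historical controls is unadjusted, so systematic differences in pre-implant severity pass straight into the estimated effect

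*Protocol*

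**What the plan says.** Section IV (Subject Selection) of the Protocol sets up a prospective interventional cohort and a retrospective control cohort. Of the controls it says: "This group will be age and sex matched with the enrolled prospective interventional patients". The Eligibility Data paragraph of Section VIII repeats that "Enrolled subjects in the prospective arm will be matched to historical controls", and Section VI (Study Procedures) gives the numbers: "We aim to enroll 25 subjects in the prospective interventional cohort, and compare to 25 subjects in the matched retrospective control cohort". No section states a matching ratio, a tolerance for age, or whether matching is patient to patient or by group distribution.

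The Primary Endpoint subsection then fixes the analysis: "The primary analysis will be performed in an intention-to-treat fashion using a two-sided T-test (alpha level=0.05". The null hypothesis concerns mean maximal 24-hour VIS. The subsection continues: "Analysis assumptions will include independence of study groups", together with a lognormal or normal shape within each group. No covariate, stratum or pair is named there, and no adjusted analysis appears elsewhere as a primary or sensitivity analysis.

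The Data Collection Schedule (Section VII) marks hemodynamics, medications and laboratory values at the pre-LVAD visit. Section VI says that data for both cohorts come from the electronic medical record.

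**The concern.** The comparison is historical and not randomised, so nothing in the design makes the two groups alike in severity beyond age and sex. The outcome is the amount of vasoactive and inotropic support. Section II (Background and Significance) itself links multi-agent support and higher VIS to right heart dysfunction and to worse creatinine, ALT and AST. By the Protocol's own account, then, these markers of severity track the endpoint. If treated patients and controls differ systematically on them before surgery, the t-test attributes the resulting VIS difference to the RVAD. The direction is unknown: it could create an apparent benefit or hide a real one.

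This cannot be left to an unseen SAP, because the Protocol itself names the test and its assumptions.

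**Working it through.** **Inputs from the Protocol.** Two-sided alpha 0.05; 80% power; 17 per group; SD 0.5; 50% reduction; 25 per group planned. **Assumed, because the documents give no figure:** the shift b in mean outcome caused by baseline imbalance (0.25 and 0.5 SD), the covariate-outcome correlation r (0.3 and 0.5), and the within-pair correlation ρ (0.1 to 0.3).

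**1. The stated sample size.** The Power Analysis says: "80% power will be generated with 2-tailed confidence interval of 0.05 from a sample size of 34 patients (17 per group". Reading the 50% reduction as a difference of 0.5 gives d = 0.5/0.5 = 1.0. An unpaired two-sample t-test (noncentral t) then needs 16.7, so 17 per group, with power 80.7% at 17. The figure reproduces as an unpaired, unadjusted calculation, so the sample size also makes no use of the matching. (On the natural-log scale, d = ln 2/0.5 = 1.39 and about 10 per group would be needed.)

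**2. Bias from imbalance.** With no true effect and a systematic shift of b SD, the t statistic has noncentrality b × √(n/2). For n = 25, √12.5 = 3.536 and the critical value on 48 df is 2.011.

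| b (SD) | noncentrality, n = 25 | rejection of a true null, n = 25 | same, n = 17 |
|---|---|---|---|
| 0 | 0 | 5% | 5% |
| 0.25 | 0.884 | 13.9% | 10.9% |
| 0.5 | 1.768 | 41.0% | 29.3% |

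To judge these shifts: a covariate with correlation r to the outcome and a standardised imbalance δ gives b = r × δ. At r = 0.5, b = 0.25 needs δ = 0.5 and b = 0.5 needs δ = 1.0. Chance imbalance is already covered by the nominal 5%, so b is the systematic part only. A larger sample makes the problem worse, as the last two columns show.

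**3. Precision.** Adjustment multiplies the SE by √(1 − r²), so the effective d is 1.0/√(1 − r²).

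| r | SE factor | effective d | power, 25 per arm |
|---|---|---|---|
| unadjusted | 1 | 1.000 | 93.4% |
| 0.3 | 0.954 | 1.048 | 95.3% |
| 0.5 | 0.866 | 1.155 | 97.9% |

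These gains assume that the arms are balanced on the covariate; with imbalance they are smaller.

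**4. Pairing, if matching is 1:1.** The true variance of the mean difference is 2σ²(1 − ρ)/n, while the unpaired test uses 2σ²/n. Its standard error is too wide and it rejects too rarely. Results for 25 pairs (alpha by simulation; power at d = 1.0):

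| ρ | actual alpha, unpaired | power, unpaired | power, paired |
|---|---|---|---|
| 0.1 | about 3.9% | 94.4% | 94.7% |
| 0.2 | about 3.0% | 95.3% | 96.6% |
| 0.3 | about 2.1% | 96.1% | 98.2% |

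**The case against.** A reader might infer that assuming independent groups flatly contradicts the matching. The documents do not support that. They never mention pairs, a ratio or calipers, and 25 against 25 fits individual or frequency matching equally well. Under frequency matching, independent groups is a defensible assumption. The firm statement is that the matching type is not given and the analysis makes no reference to it.

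A reader might also infer that the unadjusted test leaves the trial short of power. It does not under the Protocol's own inputs: power is 93% at 25 per arm with d = 1.0, and 99.8% if SD 0.5 is on the natural-log scale (d = 1.39). Nor does ignoring pairs create false positives, since that error is conservative.

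Finally, the baseline data are not wholly unused. Age and sex select the controls, and preoperative creatinine enters the AKI definition. They are absent only from the primary test.

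All three objections stand and narrow the point. None answers the main part: an unadjusted test in a non-randomised comparison matched on two demographic variables.

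**Conclusion.** The concern holds as a matter of confounding and could be cheaply reduced. Followed as written, the plan leaves any measured severity imbalance in the primary estimate. The false-positive rates of about 14% and 41% rest on assumed shifts of 0.25 and 0.5 SD. They show sensitivity and do not predict what this trial will see. The precision gain is minor: about 2 to 5 percentage points of power at d = 1.0. The effect of ignoring pairs is conservative, and arises only if matching is 1:1 and pairs are positively correlated.

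**What to change.** 1. Make the primary analysis a linear model on log maximal 24-hour VIS with terms for arm, age, sex and one prespecified severity covariate, for example inotrope use or a hemodynamic or laboratory value. Report the adjusted geometric mean ratio with its 95% CI, and keep the unadjusted t-test as a sensitivity analysis. State how a maximal VIS of zero is handled, since it has no logarithm.

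2. Fix the covariate's timing. Section V allows RVAD placement up to 48 hours before LVAD implantation, so a value taken between the two procedures is post-treatment in the intervention arm, and adjusting for it could remove part of the effect. Use a value from before RVAD placement in that arm and from the equivalent pre-LVAD time in controls. A pre-implant VIS is not a listed variable, and for outpatients the Medications paragraph records home medications at screening, so check availability before choosing.

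3. State the matching type and ratio. If it is by 1:1 pairs, add a pair term or pair-clustered errors and replace the independence-of-groups assumption. If it is by frequency, independence conditional on the covariates can stand. Deleting the independence phrase alone would settle neither case.

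Cost: a change of wording, a few degrees of freedom out of 48, and no additional patients. Adjustment removes measured confounding only; unmeasured differences between past and current patients remain.

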In some cases, right ventricular failure post-LVAD also requires mechanical circulatory support during the perioperative period. When used, these devices allow for rapid down titration of inotropic support and an increase in LVAD operation speed and therefore systemic perfusion. Newer generation, percutaneous assist devices are now available and can be positioned in the right ventricle providing up to 4.5 L/min of support. Several attempts have been made to create calculations to predict RVF in LVAD patients, with little success (Salna). Since RVF is difficult to predict and can have harmful effects such as increased ICU stay, adverse outcomes, and mortality (Anderson), it could be beneficial to preemptively treat patients through preoperative or intraoperative percutaneous right ventricular assist device (RVAD) placement to prevent RVF. The purpose of this study is to test the hypothesis that preemptive use of percutaneous RVADs will mitigate the need for inotropic support in LVAD patients, reducing associated adverse outcomes.

There are two types of percutaneous RVADs that will be used in the study: the Impella RP and the ProtekDuo. These devices allow for early intervention in RVF without the need for invasive surgical procedures requiring placement of durable RVADs via thoracotomy or sternotomy. Unplanned reoperation and implantation of surgical RVADs is associated with higher morbidity and poor outcomes (Salna). The use of percutaneous RVADs to prevent RVF requiring reoperation and durable RVADs therefore may be a safer alternative that yields better outcomes. The objective of this prospective study is to assess whether RVAD placement in patients prior to or during LVAD implantation leads to a mitigated need for vasoactive inotropic support and improved end organ function compared with standard of care LVAD implantation in the absence of percutaneous RVAD placement.

The Impella RP, manufactured by Abiomed, is a heart pump that delivers blood from the inferior vena cava (IVC) to the pulmonary artery (PA). Its insertion is done percutaneously via catheterization through the femoral vein. The use of the Impella RP device is often used for the management of RVF post-LVAD placement. In these patients, hemodynamics have been shown to improve immediately after Impella RP initiation. This includes an increase in cardiac index

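### Cox models, event rates and relative risks are prescribed for all secondary outcomes, but total VIS and LVAD speed have no event to analyse

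*Protocol*

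**What the plan says.** Protocol section VIII, Secondary Outcomes, lists eight outcomes: total VIS, ICU stay, total post-operative stay, survival at discharge, survival at 1 year, acute kidney injury (AKI), liver dysfunction and LVAD speed. The two entries at issue read "Total VIS (throughout hospitalization" (closing bracket left off here) and "LVAD device speed".

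One rule follows the list: "Cox proportional hazard models (one sided, 0.05 significance level) will be used to compare rates of secondary outcomes between intervention and historical arms". The next sentence is "Event rates and relative risks will also be estimated for each of these outcomes". No outcome is exempted, and no other method is named for the secondary outcomes.

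The same section handles the primary outcome differently. Mean maximal 24-hour VIS is compared "using a two-sided T-test (alpha level=0.05", assuming lognormal or normal data. The Power Analysis also works two-sided: "80% power will be generated with 2-tailed confidence interval of 0.05".

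**The concern.** A Cox model compares hazards, so each patient needs a follow-up time and an indicator of whether an event occurred. An event rate or relative risk needs a count of patients with an event. A VIS summed over an admission and a pump speed supply neither.

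Both outcomes bear on the study's reasoning. Total VIS extends the inotrope question beyond the first 24 hours. The Background gives "an increase in LVAD operation speed and therefore systemic perfusion" among the benefits of mechanical right-sided support. If the stated method cannot be applied, someone must choose another later. Section V says that the control cohort's clinical data already sit in a database, so that choice could be made with half the data in view.

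The one-sided level is a lesser matter. It sets a lower bar for declaring benefit on the secondary outcomes than on the primary, without explanation.

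**Working it through.** **1. The plan's own figure.** The protocol gives no power or event figure for any secondary outcome. Its only such figure is 17 per group for the primary. Inputs from the Power Analysis are SD 0.5, 80% power and two-tailed 0.05. Reading the 50% reduction as a difference of 0.5 (my assumption) gives a standardised effect of 0.5/0.5 = 1.0.

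- Two-sided, n = 2(z_alpha + z_beta)²/effect² = 2(1.960 + 0.842)²/1.0² = 15.7, so 16. The exact t-test calculation gives 16.71, so 17.
- One-sided at 0.05, n = 2(1.645 + 0.842)²/1.0² = 12.4, so 13. The exact t-test calculation gives 13.10, so 14.

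On this reading the stated 17 matches the two-sided basis only. This confirms the standard set for the primary; it does not bear on the misfit itself.

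**2. What the prescribed methods need.** The Cox model is h(t) = h0(t)·exp(b × arm), fitted to pairs of time and event indicator. The relative risk is (a/n1)/(c/n0), where a and c count patients with the event.

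**3. The eight outcomes against those needs.**

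| Outcome | Nature | Cox usable? | Event rate and relative risk usable? |
|---|---|---|---|
| Total VIS | cumulative score | no event or event time | no |
| ICU stay | duration | yes, as time to discharge alive (not stated) | no |
| Total post-operative stay | duration | yes, as time to discharge alive (not stated) | no |
| Survival at discharge | binary | not needed | yes |
| Survival at 1 year | time to event | yes | Cox is the natural method |
| AKI | defined event | yes, if event times are used | yes |
| Liver dysfunction | yes/no | not needed | yes, once defined |
| LVAD speed | device setting | no event, event time or threshold | no |

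Two of eight, total VIS and LVAD speed, fit neither method. I found no event or threshold for them elsewhere in the protocol.

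**4. Sidedness.** One-sided 0.05 has critical value z = 1.645 and a false-benefit probability of 0.05, equivalent to a two-sided 0.10 test. Two-sided 0.05 has z = 1.960 and a false-benefit probability of 0.05/2 = 0.025. The ratio is 0.05/0.025 = 2 per outcome. The direction of a hazard ratio that means benefit also varies: below 1 for death or AKI, above 1 for time to discharge alive.

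**The case against.** The best defence is that the rule was meant for event-type outcomes and that a statistical analysis plan will sort out the rest. The sentence on event rates and relative risks covers every listed outcome, so the text does not support that reading. Even if it did, two outcomes would have no stated method. Nor is this a detail left open for later: the protocol names a method, and the method is wrong for these two.

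Other parts of the defence stand, and they limit what a reader might infer:

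- **That the inotrope hypothesis goes untested.** It does not. Maximal 24-hour VIS is the primary with a suitable test, and mean and cumulative 24-hour VIS are also compared.
- **That the relative risk would come out at exactly 1.00**, with all 25 patients per arm ("We aim to enroll 25 subjects in the prospective interventional cohort", and 25 controls) counted as events. That treats having a value as the event, which the protocol nowhere says. The quantity is undefined.
- **That Cox is wrong for length of stay.** It can be used with discharge alive as the event.
- **That the differing sidedness is a contradiction, or that no direction is given.** Secondary tests may differ from the primary, and Specific Aims and Potential Benefits both state the benefit expected. Only the reason for one-sided testing is missing.
- **That the looser level moves significance thresholds by a known hazard ratio.** The protocol gives no event counts, so any such threshold would rest on invented inputs.
- **That early deaths would make total VIS falsely favour the device.** Death does truncate the total, but the Background links higher VIS with hospital mortality, so the direction of the effect is unknown.

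**Conclusion.** The point holds for two of the eight secondary outcomes. For total VIS and LVAD device speed, no hazard, event rate or relative risk is defined, so the prescribed analysis cannot validly compare the arms. This follows from the wording and the nature of the outcomes, and rests on no assumed event counts or effect sizes.

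The sidedness point is minor: a 5% false-benefit rate per outcome where the primary's standard allows 2.5%, with no reason given. That figure follows from the stated levels alone.

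The primary analysis and the sample size are unaffected. This is a defect in the secondary analysis text that should be corrected before the comparison is made.

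**What to change.** Replace the single rule in Secondary Outcomes with methods assigned by outcome type.

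- **Cox models:** survival at 1 year; AKI if event times are used; ICU and total post-operative stay as time to discharge alive, with in-hospital death not counted as discharge.
- **Event rates and relative risks:** survival at discharge, AKI and liver dysfunction.
- **Total VIS:** a two-sample comparison, either a t-test on the log scale, in line with the lognormal assumption for the primary VIS, or a rank test. Report in-hospital deaths alongside, because death truncates the total. Dividing by days alive in hospital is not a good substitute: for the same total it scores a shorter stay as worse, and a shorter stay is a hypothesised benefit.
- **LVAD speed:** means or ranks at a named time point. The Data Collection Schedule has a Device Details row at 3 months, 6 months and 1 year, but the protocol does not say that it contains speed. The Background's reasoning about speed concerns the perioperative period, and an early postoperative reading would have to be extracted from the medical record.
- **Level:** two-sided 0.05 with 95% confidence intervals throughout, or a stated reason for one-sided tests with the direction given for each outcome.

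The cost is slightly more analysis work, possible record extraction for speed, and a stricter nominal threshold for benefit. Enrolment and treatment do not change.
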